14.12.18 Non-ICH Listings

Non-IC	Non-ICH: Listings						
No.	Population	IDSL / Example Shell	Title	Programming Notes	Deliverable [Priority]		
Pharma	cokinetic						
68.	PK	PK08	Listing of Plasma GSK2838232 PK Concentration-Time Data – Part 1A	Sort by participant, treatment, day, and time	SAC [1]		
69.	PK	PK08	Listing of Plasma GSK2838232 PK Concentration-Time Data – Part 1B	Sort by participant, treatment, day, and time	SAC [1]		
70.	PK	PK07	Listing of Plasma GSK2838232 PK Concentration-Time Data – Part 2	Sort by participant, treatment, day, and time	SAC [1]		
PK Stat	PK Statistical Analysis						
71.	PK	SAS output of Table5.6	SAS Output of Summary Results of GSK2838232 PK Parameter Treatment Comparisons for the Relative Bioavailability – Part 1A		SAC [1]		
72.	PK	SAS output of Table 5.10	SAS Output of Summary Results of GSK2838232 PK Parameter Treatment Comparisons for the Food Effect – Part 1B		SAC [1]		
73.	PK	SAS output of Table 5.16	SAS Output of Summary Results of Steady-State GSK2838232 Concentrations Assessment – Part 2		SAC [1]		
74.	PK	SAS output of Table 5.17	SAS Output of Summary Results of GSK2838232 PK Parameter Treatment Comparisons – Accumulation Ratio – Part 2		SAC [1]		

14.13 Appendix 13: Example Mock Shells for Data Displays

Example: Non-Standard1 Page 1 of n

Protocol: XXXXXX Page 1 of 1

Population: PK Parameter

Geometric LSMean 90% Confidence Interval Comparison PK Parameter Test/Ref. (N=12)(N=12)Ratio CVw (%) AUC (0-inf) (h*ng/mL) G vs A 1029.925 1469.603 1.4269 (1.1962,1.7021) 24.18 AUC (0-t) (h*ng/mL)989.181 1443.028 1.4588 (1.2320,1.7274) 23.14 G vs A AUC (0-24) (h*ng/mL) G vs A 460.663 681.540 1.4795 (1.2479,1.7541) 23.32 Cmax (ng/mL) G vs A 30.126 47.561 1.5787 (1.3118,1.9000) 25.43 21.782 1.4161 (1.2044,1.6649) 22.14 C24 (ng/mL) G vs A 15.382 t1/2 (h) G vs A 19.770 18.779 0.9499 (0.8578,1.0519) 13.85

A: Treatment description G:Treatment description

CONFIDENTIAL

205820

Example: Non-Standard2 Page 1 of n

> Protocol: XXXXXX Population: PK Parameter Page 1 of 1

Table X.XX
Summary Results of Treatment Comparisons for the Food Effect - Part 1B

Geometric LSMean

PK Parameter	Comparison Test/Ref.		F =11) Ratio	90% Confidence Interval	CVw (%)
AUC (0-inf) (h*ng/mL)	F (Fed) Vs G (Faste	1) 1469.603 232		(1.4120,1.7768)	
AUC (0-t) (h*ng/mL)	F (Fed) Vs G (Faste	1443.028 229	9.310 1.5934	(1.4185,1.7899)	15.13
AUC (0-24) (h*ng/mL)	F (Fed) Vs G (Faste	d) 681.540 104	8.089 1.5378	(1.3761,1.7185)	14.50
Cmax (ng/mL)	F (Fed) Vs G (Faste	47.561 7	7.132 1.6217	(1.3762,1.9111)	21.81
C24 (ng/mL)	F (Fed) Vs G (Faste	i) 21.782 3	5.718 1.6398	(1.4417,1.8653)	16.80
t1/2 (h)	F (Fed) Vs G (Faster	18.779 1	8 582 0 9895	(0.9155,1.0695)	10.14

G: GSKXXXXXX Capsule 100mg + XXX F: GSKXXXXXX Capsule 100mg + Food + XXX

CONFIDENTIAL

205820

Page 1 of n Example: Non-Standard3

> Protocol: XXXXXX Population: PK Parameter Page 1 of 1

Table X.XX
Summary Results of GSK XXXXXXX PK Parameter Treatment Comparisons - Accumulation Ratio - Part 2

		Treatment	Comp Tes					_Geometri Ref.	c LSmean_ Test.	Ratio	90% Confidence Interval	CVb(%)
Accumulation AUC(0-tau)	Ratio	RD20mg+RTV	Day	11	vs	Day	1	175.060	449.021	2.5650	(1.9931,3.3008)	21.94
		RD50mg+RTV	Day	11	VS	Day	1	265.413	1087.465	4.0973	(2.7102, 6.1943)	36.68
		CapRD100mg+RTV				Day		635.446	2411.467	3.7949	(2.8185, 5.1096)	25.99
		CapRD200mg+RTV				Day		1056.386	4014.085	3.7998	(3.1234, 4.6227)	16.97
		CapRDQ12H200mg				Day		267.134	742.180	2.7783	(2.3991, 3.2175)	12.67
Accumulation Cmax	Ratio	RD20mg+RTV	Day	11	VS	Day	1	11.109	25.335	2.2807	(1.6717,3.1114)	27.18
		RD50mg+RTV	Day	11	VS	Day	1	17.098	56.614	3.3111	(2.2479.4.8771)	34.23
		CapRD100mg+RTV				Day		46.172	129.785	2.8109	(2.0427, 3.8681)	27.97
		CapRD200mg+RTV				Day		75.033	224.886	2.9972	(2.4531, 3.6619)	17.35
		CapRDQ12H200mg				Day		51.237	96.085	1.8753	(1.6520,2.1288)	10.93
Accumulation Ctau	Ratio	RD20mg+RTV	Day	11	VS	Day	1	5.673	14.525	2.5604	(2.0159, 3.2521)	20.77
CLau		RD50mg+RTV	Day	11	VS	Dav	1	8.919	37.403	4.1939	(2.8754, 6.1169)	33.31
		CapRD100mg+RTV				Day		20.560	78.196	3.8033	(2.6625, 5.4329)	31.39
		CapRD200mg+RTV				Day		36.696	136.681	3.7247	(2.9585, 4.6892)	19.99
		CapRD012H200mg				Day		18.364	39.144	2.1315	(1.7403, 2.6107)	17.56
		CaphoQiziizoomg	Day	TI	42	Day	_	10.504	22.144	2.1313	(1.7903,2.0107)	11.30

CONFIDENTIAL

205820

Example: Non-Standard4 Page 1 of n

Protocol: XXXXXX Page 1 of 2 Population: PK Parameter

Table X.XX

Summary Results of Steady-State GSKXXXXXXX Concentrations Assessment - Part 2

Included Days	Treatment	Slope	90% Confidence Interval
Days 3-11	RD20mg+RTV	0.023	(0.009,0.037)
	RD50mg+RTV	0.082	(0.065,0.100)
	CapRD100mg+RTV	0.058	(0.044,0.072)
	CapRD200mg+RTV	0.033	(0.018,0.047)
	CapRD212H200mg	0.007	(-0.005,0.019)
Days 4-11	RD20mg+RTV	0.006	(-0.009,0.020)
	RD50mg+RTV	0.063	(0.046,0.081)
	CapRD100mg+RTV	0.037	(0.022,0.051)
	CapRD200mg+RTV	0.003	(-0.008,0.015)
	CapRDQ12H200mg	0.004	(-0.010,0.018)
Days 5-11	RD20mg+RTV	-0.012	(-0.029,0.005)
	RD50mg+RTV	0.038	(0.022,0.053)
	CapRD100mg+RTV	0.013	(-0.001,0.027)
	CapRD200mg+RTV	-0.004	(-0.018,0.010)
	CapRDQ12H200mg	0.001	(-0.019,0.020)
Days 6-11	RD20mg+RTV RD50mg+RTV CapRD100mg+RTV CapRD200mg+RTV	-0.021 0.029 0.008 -0.009	(-0.041,-0.001) (0.010,0.048) (-0.011,0.028) (-0.027,0.009) (-0.022,0.025)

PAREXEL International Statistical Analysis Plan Addendum

STATISTICAL ANALYSIS PLAN ADDENDUM

205820

Reporting and Analysis Plan for: A Two Part Study to Assess i) the Relative Bioavailability and Food Effect of a Novel Tablet Formulation of Boosted-GSK2838232 Compared to Capsule and ii) the Safety and Pharmacokinetics of Repeated Once-Daily Doses of Non boosted GSK2838232

Version: Final 1.0

Date: 16/Apr/2018

GlaxoSmithKline Research & Development Limited 205820

Final 1.0

16/Apr/2018

Statistical Analysis Plan Addendum

REVISION HISTORY

Version	Version Date	Author	Summary of Changes Made
Final 1.0	See Footer	PPD	New Document

GlaxoSmithKline Research & Development Limited 205820

Final 1.0

16/Apr/2018

Statistical Analysis Plan Addendum

SIGNATURE PAGE - GLAXOSMITHKLINE RESEARCH & DEVELOPMENT LIMITED

Declaration

1. STATISTICAL ANALYSIS PLAN ADDENDUM

The Statistical Analysis Plan (SAP) Addendum details the changes and/or additional analyses required that are not currently described in the final RAP Version **1.0** dated 07/Dec/2017. The SAP Addendum describes any deviations from the planned analyses, additional analyses and if applicable, new Tables, Listings and Figures (TLFs) that are to be produced.

As Sponsor (GlaxoSmithKline Research & Development Limited) does not have any template available for RAP Addendum, PAREXEL Template of SAP Addendum is used to document the changes after database lock and finalization of the RAP.

GlaxoSmithKline Research & Development Limited 205820

Final 1.0

16/Apr/2018

Statistical Analysis Plan Addendum

2. OVERVIEW OF CHANGES REQUIRED

2.1 Summary of Changes

- Secondary end point is considered as pre-dose concentration on days 3 to 11 rather than pre-dose concentration on day 2 to 11. This is applicable to final RAP Sections 2.2, 2.4 and 9.2.5
- PK parameter Ctrough is calculated for days 3 to 11 rather than for days 2 to 11. This is applicable to final RAP Sections 9.1.1.2, and 9.2.1.2
 - However Ctrough should not be considered as PK Parameter of the study and this should not be included in ADPP dataset and those values can only be used from ADPC dataset directly and use for Steady State Assessment only. No summary statistics will be provided for this PK parameter.
- Part 2 treatments is changed as Treatment R = GSK2838232 500 mg tablet fed rather than D=GSK2838232 500 mg/r tablet fed and Treatment P=Placebo than Treatment E=Placebo. This is applicable to final RAP Section 2.3
- Listing and summary of the protocol deviation should be presented for all Important Protocol Deviation rather than all Protocol Deviation. This is applicable to final RAP section 6.5.
- For each of the PK parameters given in section of RAP, for the summary statistics calculation, geometric mean associated with 95% CI should be calculated for each treatment group; however in RAP geometric mean associated with 90% CI should be calculated for each treatment group for the summary statistics. This is applicable to RAP sections 9.1.1.2 and 9.2.1.2
- In the statistical methodology, analysis for the steady state assessment should only be mentioned as predose concentrations from days 3 to 11, and no Ctrough or Ctau terminology will be considered for this analysis.

There will be no changes to the structure/format of the tables, figures and listings based on this change. The details of these changes are provided from sections 2.2 to 2.9 below. Details of the changes in the Tables, Listings and Figures are mainly due to clarity purpose (added more clarity in title, and programming notes) as well as some Tables and Listings are clubbed for better presentation, and hence due to that number of the tables, listings and figures are changed.

GlaxoSmithKline Research & Development Limited 205820

Final 1.0

16/Apr/2018

Statistical Analysis Plan Addendum

2.2 Study objective and secondary end point

In the final SAP Section **2.2** in the secondary objective section of part 2 is stated that secondary endpoint is predose concentration on days 2 to 11. However, for the final analyses secondary endpoint is considered as pre-dose concentration on day 3 to 11.

2.3 Study Design

In the final SAP Section 2.3 in treatment assignment section it is stated that Part 2 treatment section states as below:

"Part 2 treatments:

Treatment D = GSK2838232 500 mg (as 5 x 100 mg) tablet formulation, fed, normal fat (i.e., approximately 30%) meal (reference).

Treatment E = Placebo

However this should be like this:

"Part 2 treatments:

Treatment $R = GSK2838232\ 500\ mg$ (as 5 x 100 mg) tablet formulation, fed, normal fat (i.e., approximately 30%) meal.

Treatment P = Placebo

2.4 Statistical Hypothesis/Statistical Analysis

For Part 2 study state assessment in the RAP section 2.4 it is stated as below:

Mean plasma GSK2838232 pre-dose values between Days 2 through 11 and $C\tau$ of Day 11 will be plotted against time.

However it should be as below:

Mean plasma GSK2838232 pre-dose values between Days 3 through 11 and $C\tau$ of Day 11 will be plotted against time.

2.5 Study Treatment and Sub-group Display Descriptors

In the RAP Section 5.1 Part 2 treatment group descriptors are given as below:

GlaxoSmithKline Research & Development Limited 205820

Final 1.0

16/Apr/2018

TP-EP.BS-WW-008-04 Effective date: 29 Jul 15

Statistical Analysis Plan Addendum

Treatment Group Descriptions – Part 2						
	RandAll NG Data Displays for Reporting					
Code	Description	Description	Order in TFL			
Т3	GSK2838232 500 mg (as 5 x 100 mg) tablet formulation, fed, normal fat (i.e., approximately 30%) meal (reference).	GSK 500 mg/r tablet fed	2			
P	Placebo	Placebo	1			

However it should be as follows:

GlaxoSmithKline Research & Development Limited 205820

Final 1.0

16/Apr/2018

Statistical Analysis Plan Addendum

Treatment Group Descriptions – Part 2						
	RandAll NG Data Displays for Reporting					
Code	Description	Description	Order in TFL			
Т3	GSK2838232 500 mg (as 5 x 100 mg) tablet formulation, fed, normal fat (i.e., approximately 30%) meal (reference).	GSK 500 mg tablet fed	2			
P	Placebo	Placebo	1			

2.6 Concomitant Medications

As per RAP Section 6.4 it is stated that "in the summary of concomitant medications, the ingredients will be summarized by the base only, using CMBASECD and CMBASE". However this is not followed.

2.7 Treatment Compliance and Protocol Deviations

In RAP Section 6.5 it is stated below:

"Information of each participant not received the correct treatment during each treatment period, the reason for not receiving the correct treatment, and any other protocol deviations will be summarized by treatment sequence/group and overall of each part, and listed by participant and period (treatment). In addition, a listing will be provided including dose administered along with dosing dates and time for the investigational product. However it should be as below:

Information of each participant not received the correct treatment during each treatment period, the reason for not receiving the correct treatment, and any other important protocol deviations will be summarized by treatment and overall of each part if enough important protocol deviations occur, and listed by participant and period (treatment). In addition, a listing will be provided including dose administered along with dosing dates and time for the investigational product.

2.8 Derived Pharmacokinetic Parameters

In final RAP section 9.1.1.2, details of derived pharmacokinetic parameter are given as follows:

Parameter	Parameter Description		
AUC(0-τ)	Area under the plasma drug concentration-time curve from pre-dose to the end of the dosing interval (where τ = 24 h) (Day 1 and Day 11)		
AUC(0-∞)	Area under the concentration-time curve extrapolated to infinity will be calculated as:		
	$AUC = AUC(0-last) + C(last) / lambda_z$		

GlaxoSmithKline Research & Development Limited 205820

Final 1.0

16/Apr/2018

TP-EP.BS-WW-008-04 Effective date: 29 Jul 15

Statistical Analysis Plan Addendum

Parameter	Parameter Description
Cmax	Maximum observed concentration, determined directly from the concentration-time data. (Day 1 and Day 11)
Tmax	Time of occurrence of Cmax, determined directly from the concentration-time data (Day 1 and Day 11)
Tlag	Lag-time (time delay between drug administration and first observed concentration), determined directly from the concentration-time data (Day 1)
Tlast	Time of last quantifiable concentration, determined directly from the concentration-time data (Day 11)
t½	Apparent terminal phase half-life, calculated as; t½ = ln2 / lambda_z (Day 11)
Ст	Observed concentration at the end of the dosing interval, determined directly from the concentration-time data (where $\tau = 24$ h) (Day 1 and Day 11)
Ctrough	Observed pre-dose concentrations on Days 3 to 11, determined directly from the concentration-time data

NOTES: C24, $C\tau$ and Ctrough will be extracted from the concentration data by Clinical Statistics group and merged with other calculated PK parameters provided by CPMS.

All the derived parameters described above will be listed. For each of these parameters, except tmax and tlag, the following summary statistics will be calculated for each treatment group: n, arithmetic mean, standard deviation (SD), median, minimum, maximum, geometric mean with associated 90% CI, standard deviation of logarithmically transformed data, and the between-participant CV (%CVb) based on the geometric mean for the loge-transformed PK parameters. For tmax and tlag, N, n, median, maximum, minimum, arithmetic mean and standard deviation will be calculated.

However this should be as below:

Parameter	Parameter Description
AUC(0-τ)	Area under the plasma drug concentration-time curve from pre-dose to the end of the dosing interval (where τ = 24 h) (Day 1 and Day 11)
AUC(0-∞)	Area under the concentration-time curve extrapolated to infinity will be calculated as: $AUC = AUC(0-last) + C(last) / lambda_z$
Cmax	Maximum observed concentration, determined directly from the concentration-time data. (Day 1 and Day 11)
Tmax	Time of occurrence of Cmax, determined directly from the concentration-time data (Day 1 and Day 11)
Tlag	Lag-time (time delay between drug administration and first observed concentration), determined directly from the concentration-time data (Day 1)
Tlast	Time of last quantifiable concentration, determined directly from the concentration-time data (Day 11)
t½	Apparent terminal phase half-life, calculated as; $t\frac{1}{2} = \ln 2 / \text{lambda} z \text{ (Day 11)}$
Сτ	Observed concentration at the end of the dosing interval, determined directly from the

GlaxoSmithKline Research & Development Limited 205820

Final 1.0

16/Apr/2018

TP-EP.BS-WW-008-04 Effective date: 29 Jul 15

Statistical Analysis Plan Addendum

Parameter	Parameter Description		
	concentration-time data (where $\tau = 24 \text{ h}$) (Day 1 and Day 11)		

NOTES: C24, and Cτ will be extracted from the concentration data by Clinical Statistics group and merged with other calculated PK parameters provided by CPMS.

All the derived parameters described above will be listed. For each of these parameters, except tmax and tlag, the following summary statistics will be calculated for each treatment group: N, n, arithmetic mean, standard deviation (SD), median, minimum, maximum, geometric mean with associated 95% CI, standard deviation of logarithmically transformed data, and the between-participant CV (%CVb) based on the geometric mean for the loge-transformed PK parameters. For tmax and tlag, N, n, median, maximum, minimum, arithmetic mean and standard deviation will be calculated.

2.9 Statistical Analysis/Method

Part 2

Parameter	Parameter Description
Ctrough	Observed pre-dose concentrations on Days 3 to 11, determined directly from the concentration-time data
Ro[AUC(0- τ)]	Accumulation ratio based on AUC(0- τ), determined by; Day 11 AUC(0- τ) / Day 1 AUC(0- τ)
R(Cmax)	Accumulation ratio based on Cmax, determined by; Day 11 Cmax / Day 1 Cmax
R(Cτ)	Accumulation ratio based on Cτ, determined by; Day 11 Cτ / Day 1 Cτ

NOTES:

- Additional parameters may be included as required.
- Cτ, and Ctrough will be extracted from the concentration data by Clinical Statistics group and merged with other calculated PK parameters provided by CPMS.

All the derived parameters described above will be listed. For each of these parameters, except tmax and tlag, the following summary statistics will be calculated for each treatment group: n, arithmetic mean, standard deviation (SD), median, minimum, maximum, geometric mean with associated 90% CI, standard deviation of logarithmically transformed data, and the between-participant CV (%CVb) based on the geometric mean for the loge-transformed PK parameters. For tmax and tlag, N, n,median, maximum, minimum, arithmetic mean and standard deviation will be calculated.

However is should be as follows:

Part 2

Parameter	Parameter Description
Ro[AUC(0-τ)]	Accumulation ratio based on AUC(0- τ), determined by; Day 11 AUC(0- τ) / Day 1 AUC(0- τ)

GlaxoSmithKline Research & Development Limited 205820

Final 1.0

16/Apr/2018

TP-EP.BS-WW-008-04 Effective date: 29 Jul 15

Statistical Analysis Plan Addendum

Parameter	Parameter Description
R(Cmax)	Accumulation ratio based on Cmax, determined by; Day 11 Cmax / Day 1 Cmax
R(Cτ)	Accumulation ratio based on $C\tau$, determined by; Day 11 $C\tau$ / Day 1 $C\tau$

NOTES:

- Additional parameters may be included as required.
- Cτ will be extracted from the concentration data by Clinical Statistics group and merged with other calculated PK parameters provided by CPMS.

All the derived parameters described above will be listed. For each of these parameters, except tmax and tlag, the following summary statistics will be calculated for each treatment group: N, n, arithmetic mean, standard deviation (SD), median, minimum, maximum, geometric mean with associated 95% CI, standard deviation of logarithmically transformed data, and the between-participant CV (%CVb) based on the geometric mean for the loge-transformed PK parameters. For tmax and tlag, N, n,median, maximum, minimum, arithmetic mean and standard deviation will be calculated.

As per final RAP Section 9.2.5, statistical methodology section of Part 2 Steady State Assessment, end point or variable is given as GSK2838232 pre-dose values between Days 2 through 11, however it should be GSK2838232 pre-dose values between Days 3 through 11.

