- 7. Plasma PK samples for GSK2838232 will be collected as follows: Day 1; pre-dose (within 15 minutes prior to dosing) and 0.5,1, 1.5, 2, 2.5, 3, 3.5, 4, 6, 8, 12 and 24 h post-dose (prior to Day 2 dose). Days 3 to 10 pre-dose (within 15 minutes prior to dosing). Day 11; pre-dose (within 15 minutes prior to dosing) and 0.5, 1, 1.5, 2, 2.5, 3, 3.5, 4, 6, 8, 12, 24, 36, 48, 72, 96 and 120 h post-dose. Samples will be acidified with an equal volume of 50 mmol citrate acid buffer pH 4.0.
- 8. An AE enquiry will be made at each visit, participants will be asked if they have experienced any neuropsychiatric adverse events, including psychosis or altered mental status. (see guidance for grading Altered Mental Status in Appendix 4).
- 9. Participants will be discharged after all study procedures are completed on the morning of Day 13 (after the 48 h post-final dose sample time point) with instructions to return fasted on the mornings of Day 14 for 72 h PK sample, Day 15 for 96 h PK sample, and Day 16 for 120 h PK sample.

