10.4.2.3. Steady State Assessments

For Part 2, mean plasma GSK2838232 pre-dose values between Days 2 through 11 and $C\tau$ of Day 11 will be plotted against time. Achievement of plasma GSK2838232 steady-state will be assessed by calculating the 90% CI of the slope of the linear regression of log $(C\tau)$ versus time. The dependent variable in the linear regression model will be log $(C\tau)$ and the model will include a random intercept effect for participant and a fixed slope effect for study day. Steady state will be reached if the 90% CI for the slope estimate includes zero.

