9.2.5 Statistical Analyses / Methods

Details of the planned displays are provided in Appendix 12: List of Data Displays and will be based on GSK Data Standards and statistical principles.

Unless otherwise specified, endpoints / variables defined in Section 9.2.1 will be summarised using descriptive statistics, graphically presented (where appropriate) and listed.

Statistical Methodology Specification

Part 2 Steady State Assessments

Endpoint / Variables

GSK2838232 pre-dose values between Days 2 through 11

Model Specification

• Achievement of plasma GSK2838232 steady-state will be assessed by calculating the 90% CI of the slope of the linear regression of $\log_e(C\tau)$ versus time. The dependent variable in the mixed effect model will be $\log_e(C\tau)$ and the model will include a random intercept effect for participant and a fixed slope effect for study day. Day will be treated as a continuous variable in the model.

Model Checking & Diagnostics

- Model assumptions will be applied, but appropriate adjustments may be made based on the data.
- The Kenward and Roger method for approximating the denominator degrees of freedom and correcting for bias in the estimated variance-covariance of the fixed effects will be used.
- An unstructured covariance structure for the R matrix will be used by specifying 'type=UN' on the REPEATED line.
- In the event that this model fails to converge, alternative correlation structures may be considered such as CSH or CS.
- Akaike's Information Criteria (AIC) will be used to assist with the selection of covariance structure.
- Normality assumptions underlying the model used for analysis will be examined by obtaining a
 normal probability plot of the residuals and a plot of the residuals versus the fitted values (i.e.
 checking the normality assumption and constant variance assumption of the model
 respectively) to gain confidence that the model assumptions are reasonable.
- If there are any departures from the distributional assumptions, alternative models will be explored using appropriate transformed data.

Model Results Presentation

- Steady state will be reached if the pre-dose concentration slope estimate is close to zero or the 90% CI for the slope estimate includes zero.
- Mean plasma GSK2838232 pre-dose values between Days 2 through 11 and C_{τ} of Day 11 will be plotted against time on linear and semi-logarithmic scale..

Subgroup Analyses

Not applicable

Sensitivity and Supportive Analyses

Not applicable

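### The steady-state slope model leaves out the Day 11 24 h trough, which is collected and plotted; entering it as Day 12 would cut the slope SE by about 15% to 21% at no sampling cost

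*SAP*

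**What the plan says.** Protocol 10.4.2.3 assesses steady state by "calculating the 90% CI of the slope of the linear regression of log" Cτ against time, and specifies that "the model will include a random intercept effect for participant and a fixed slope effect for study day". Steady state is taken as reached if that interval covers zero. SAP 9.2.5 repeats the model and names the variable as pre-dose values on Days 2 to 11.

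The addendum moves the start to Day 3. Addendum 2.1 says that "analysis for the steady state assessment should only be mentioned as predose concentrations from days 3 to 11" and drops the Ctrough and Cτ terms from this analysis. Addendum 2.9 makes the same correction to SAP 9.2.5: "it should be GSK2838232 pre-dose values between Days 3 through 11".

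The plot goes one point further. SAP 9.2.5 has "Mean plasma GSK2838232 pre-dose values between Days 2 through 11 and" Cτ of Day 11 plotted against time, and Addendum 2.4 keeps that point: "pre-dose values between Days 3 through 11 and $C\tau$ of Day 11 will be plotted against time".

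The sample is scheduled. Footnote 7 to protocol Table 3 lists, for Part 2, "Day 11; pre-dose (within 15 minutes prior to dosing) and 0.5, 1, 1.5, 2, 2.5, 3, 3.5, 4, 6, 8, 12, 24" and later hours. The same footnote describes the Day 1 sample at "24 h post-dose (prior to Day 2 dose"), so the plan already lets a 24 h post-dose sample serve as the next day's trough.

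The SAP's parameter tables define Cτ as the end-of-interval concentration with τ = 24 h, on Days 1 and 11.

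**The concern.** The 24 h value after the Day 11 dose is a trough of the same kind as the pre-dose values: one full dosing interval after a 500 mg or lower once-daily dose. It is also literally the Cτ that the protocol names as the dependent variable. As the last point of any window it would share the greatest leverage on the slope with the first point. Leaving it out gives up precision in a cohort with only 6 active participants. It also means that the plot and the model behind the steady-state statement rest on different data, with no explanation.

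**Working it through.** **Inputs.** 6 active participants (protocol 10.1). Random intercept and common slope (protocol 10.4.2.3). 90% CI. Windows starting on Days 3, 4, 5 and 6 and ending on Day 11 appear in the example shell for the steady-state table (SAP Appendix 13); the SAP text does not fix them. The documents give no precision for this slope and no within-subject SD for troughs, so there is no plan figure to reproduce and every SD below is an assumption.

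**Formula.** For balanced data with independent, equal-variance residuals, SE(slope) = σ / √(n·Sxx), where Sxx = Σ(day − mean day)². With k days, df = 6k − 7 and the 90% half-width is t(0.95, df) × SE. The SE ratio with and without the extra point is √(Sxx without / Sxx with), which does not depend on σ.

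| Window start | Sxx to Day 11 | Sxx with Day 12 | SE ratio | SE reduction |
|---|---|---|---|---|
| Day 3 | 60 | 82.5 | 0.853 | 15% |
| Day 4 | 42 | 60 | 0.837 | 16% |
| Day 5 | 28 | 42 | 0.816 | 18% |
| Day 6 | 17.5 | 28 | 0.791 | 21% |

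Put the other way, the SE without the point is 1.17 to 1.27 times (1/0.853 to 1/0.791) what it would be with it.

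**Example half-widths per day.**
- From Day 3 (df 47, then 53): 0.0133 falls to 0.0113 at SD 0.15, and 0.0265 to 0.0226 at SD 0.30.
- From Day 6 (df 29, then 35) at SD 0.2: 1.699 × 0.2/√(6 × 17.5) = 0.0332 falls to 1.690 × 0.2/√(6 × 28) = 0.0261.

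**Autocorrelation.** With AR(1) residuals the excess SE without the point shrinks. Across the four windows it is 16% to 23% at ρ = 0.3, 13% to 19% at ρ = 0.6, and 8% to 12% at ρ = 0.9.

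**Effect on the steady-state call.** Trials were simulated (20,000 per scenario) with exponential accumulation at the unboosted half-life of 15 to 18 h (protocol 3.2.1). The probability that the 90% CI includes zero, without and then with the extra trough, was:

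| Half-life, assumed SD | Window start | Without | With |
|---|---|---|---|
| 15 h, 0.10 | Day 3 | 0.438 | 0.459 |
| 18 h, 0.15 | Day 3 | 0.401 | 0.418 |
| 18 h, 0.15 | Day 4 | 0.810 | 0.812 |
| 18 h, 0.15 | Day 6 | 0.899 | 0.897 |
| 18 h, 0.20 | Day 3 | 0.576 | 0.601 |

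The last row, 2.5 points, is the largest move among these; simulation error on such a difference is up to about 0.5 point (√(2 × 0.24/20,000)). The call barely moves because the added point lies on the flat part of the curve and pulls the slope down along with its SE. At 18 h from Day 3, the mean slope falls from 0.0156 to 0.0130 per day.

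**Sustained drift.** If troughs kept rising linearly at an assumed 0.02 per day on the log scale (SD 0.15, from Day 6), the slope would not shrink:
- Without: SE = 0.15/√105 = 0.0146, noncentrality 0.02/0.0146 = 1.37, probability that the CI includes zero 0.62.
- With: SE = 0.15/√168 = 0.0116, noncentrality 1.73, probability 0.48.

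**The case against.** The strongest reply is that the choice follows the protocol. The secondary endpoint is pre-dose concentrations on Days 2 to 11, protocol 10.4 speaks of the slope of pre-dose concentrations, and protocol 10.4.2.3 assigns the Day 11 Cτ explicitly only to the plot. That stands, so a reader who infers a breach of the protocol goes further than the text allows. It does not make the 24 h value unsuitable.

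A reader might also infer that the wider interval makes a false steady-state finding easier, with the late windows worst affected. At 15 to 18 h the simulations do not support this: from Day 3 the extra point slightly raises the chance that the interval covers zero, and from Day 6 both versions sit near 0.90. A larger fall, from 0.49 to 0.43 (from Day 6, SD 0.15), appears at a half-life of 42 h, which belongs to ritonavir-boosted dosing; Part 2 is unboosted.

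Because the addendum records changes made after database lock, a reader might suspect that the point was removed once data were seen. The documents do not show that: SAP 9.2.5 already named a variable ending with the Day 11 pre-dose value.

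Two limits on the size also stand. The first-choice unstructured residual matrix for 9 days has 9 × 10/2 = 45 parameters against 6 active participants, so the ratios presume a simpler fallback structure. And the SAP describes the analysis as descriptive, with no formal hypothesis.

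**Conclusion.** The point holds as lost precision and a mismatch between plot and model, not as an error that alters the steady-state conclusion. With independent residuals, omitting the Day 11 24 h trough costs a slope SE reduction of about 15% (from Day 3) to 21% (from Day 6), and less under autocorrelation. At the documented unboosted half-life the chance of declaring steady state changes by about 2 points or less, in either direction. Detection improves materially only for a sustained late drift, as in the assumed 0.02 per day case. These sizes rest on 6 active participants with complete data, an estimable simple covariance, and windows taken from an example shell. Adding the point does not mend the rule itself, under which an imprecise slope favours a steady-state finding.

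**What to change.** In SAP 9.2.5 and Addendum 2.1 and 2.9, define the modelled values as pre-dose concentrations from Day 3 through Day 11 plus the Day 11 24 h concentration, entered as Day 12. End any windows reported in Table 5.18 at that point and label them accordingly. State that this adds one trough to the protocol's endpoint wording, and keep the Days 3 to 11 slope as a supportive result. If the sponsor prefers the present model, one sentence saying why the point is plotted but not modelled would settle the inconsistency, though not the precision.

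The cost is a short text change, one extra record per active participant in the analysis dataset, and new window labels. No new samples or visits are needed. Because the addendum post-dates database lock, the change should be dated and justified there as such.
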